4.3. Sample Size and Power Considerations

The primary endpoint for this study is the change from baseline to Week 52 in the 6MWD.

Using a 2-group t-test with a 1-sided significance level of 0.025 and a 2:1 randomization ratio, a total of 99 subjects (66 subjects in the ATB200/AT2221 group and 33 subjects in the alglucosidase alfa/placebo group) would yield approximately 90% power to detect a clinically meaningful standardized effect size of 0.7 between the 2 groups in a superiority test for the primary endpoint. This calculation was performed using nQuery 8[®].

Assuming a 10% dropout rate (after randomization), a total of approximately 110 subjects were planned to be randomized to ensure 99 evaluable patients.

Details of the sample size justification are described in [Appendix 1](#).

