8.5. Analysis of the Primary Efficacy Endpoint

8.5.1. Primary Efficacy Analysis

The primary efficacy endpoint (change from baseline to Week 52 in 6MWD) will be analyzed using an MMRM model to compare between treatment and control on the ITT-OBS population.

For this analysis, the dependent variable is the change from baseline to all post-baseline visits. Independent variables in the model are the fixed, categorical effects of treatment, time (ie, visit), treatment-by-time interaction, ERT status, and gender, as well as the fixed, continuous covariates of baseline 6MWD, baseline age, baseline weight, and baseline height. SAS PROC MIXED will be used for the analysis, with restricted maximum likelihood estimation (REML) and unstructured within-subject covariance structure. The Kenward-Roger approximation will be used to estimate denominator degrees of freedom and adjust standard errors for the tests of fixed effects. If this model fails to converge, a compound symmetry (CS) covariance structure will be used instead. The OBSMARGINS (OM) option in the LSMEANS statement will be specified to allow for the use of the observed marginal distributions of the categorical variable rather than assuming a balance among the levels of the categorical variable. The E option will also be specified to check for estimability of LS means.

All the relevant estimates from this model, including LS means, standard errors (SE), treatment differences in LS means, and the corresponding 95% CIs will be estimated for each time point. The main variable to be estimated (ie, the estimand) in the primary comparison is the difference between ATB200/AT2221 and alglucosidase alfa/placebo in mean change in 6MWD from baseline to Week 52, regardless of whether intercurrent events have occurred. The significance test will be based on the treatment comparison of LS means at Week 52 and a p-value will be presented for this time point only. Estimated LS means (\pm SE) for the change from baseline by treatment group will be plotted over time.

Exploratory Interaction Tests:

The study is not powered to detect any interaction. However, the following interactions will be explored.

Time-based interactions (ie, time-by-baseline 6MWD, time-by-baseline age, time-by-baseline weight, time-by-ERT status) will be examined separately (one at a time) in separate MMRM models to understand the changes over time.

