APPENDIX 3. SAMPLE SAS PROGRAMS

All analysis programs will be submitted. Three sample SAS codes are provided below to illustrate the MMRM analysis (based on ITT-OBS), ANCOVA (based on ITT-LOCF) and the composite endpoint analysis that combines two separate logistic regression analyses.

Sample Code for the MMRM Analysis

```
/******  
/** Description: Sample program for implementing the MMRM Analysis. */  
/** This sample program applies to the primary analysis of the primary */  
/** endpoint(6MWD), and can be adapted to all other MMRM analyses */  
/** specified in the SAP. */  
/* */  
/* Response variable(CHG): Change from baseline at each visit timepoint*/  
/** Explanatory variables in the model are: */  
/** TRTPN AVISIT TRTPN*AVISIT SEX BASE ERTEXP AGEBL HGTBL WGTBL */  
/* */  
/* Assume that the 6MWD dataset is called ANADAT */  
/* */  
/* Some Definitions: */  
/** TRTPN = Treatment group (1 = new treatment, 2 = control) */  
/** AVISIT = Analysis Visit */  
/** ERTSTA = ERT status (Experienced or Naïve) */  
/******  
  
/******  
/* Perform the analysis. Then obtain treatment means and differences at */  
/* each visit, with p-values and CIs. */  
/******  
  
ods output LSMeans=lsm LSMEstimate=lsmest;  
proc mixed data = anadat method = reml;  
class TRTPN AVISIT ERTSTA SEX USUBJID;  
model CHG = TRTPN AVISIT TRTPN*AVISIT SEX BASE ERTSTA AGEBL HGTBL WGTBL /  
ddfm=kr;  
repeated AVISIT / type=UN subject=USUBJID;  
lsmeans TRTPN*AVISIT / slice=AVISIT alpha=0.05 OM diff cl s; *** Obtain  
treatment means and differences at each visit, with CIs.**;  
  
lsmestimate TRTPN*AVISIT "Treat vs. Control at Week 52" 0 0 0 1 0 0 0 -1  
/ upper testvalue=0; *** Get treatment diff and 1-sided p-value **;  
  
lsmestimate TRTPN*AVISIT `Treat vs. Control at Week 52' 0 0 0 1 0 0 0 -1 /  
testvalue=0 alpha=0.05 cl; **Get treatment diff and 2-sided p-value *;
```

Sample Code for the ANCOVA

```
/******  
/* ANCOVA is based on the ITT-LOCF population. This sample program can */  
/* be adapted to other ANCOVA analyses for the 6MWD, percent predicted */  
/* FVC, and all others specified in the SAP. */  
/******  
  
/* Perform the ANCOVA, obtain estimates of the treatment means, treatment */  
/* differences, p-values and 95% CIs. */  
  
ods output LSMeans=lsm LSMEstimate=lsmest;  
proc mixed data = anadat;  
  class TRTPN ERTSTA SEX;  
  model CHG = TRTPN SEX BASE ERTSTA AGEBL HGTBL WGTBL /ddfm=kr;  

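### The primary MMRM holds the baseline 6MWD slope equal at all four visits although only Week 52 is tested; a visit-specific slope would be a nearly free safeguard

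*SAP*

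**What the plan says.** SAP 8.5.1 models change from baseline at every post-baseline visit. Besides treatment and visit, the terms are "treatment-by-time interaction, ERT status, and gender, as well as the fixed, continuous covariates of baseline 6MWD, baseline age, baseline weight, and baseline height". Estimation is by "restricted maximum likelihood estimation (REML) and unstructured within-subject covariance structure". Treatment is the only factor crossed with visit. The Appendix 3 code agrees: "model CHG = TRTPN AVISIT TRTPN*AVISIT SEX BASE ERTSTA AGEBL HGTBL WGTBL" contains BASE but no BASE*AVISIT.

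Inference is at one visit: "The significance test will be based on the treatment comparison of LS means at Week 52".

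The time-by-baseline term appears only under the exploratory interaction tests of 8.5.1: "Time-based interactions (ie, time-by-baseline 6MWD, time-by-baseline age, time-by-baseline weight, time-by-ERT status) will be examined separately", one at a time, in their own MMRMs. No rule carries a finding from those models into the primary one. The supportive single-visit ANCOVA at Week 52 (SAP 8.5.1.1, Table 6) estimates its own Week 52 slope, but on ITT-LOCF data.

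**The concern.** With a main effect only, the model estimates one baseline slope as a covariance-weighted average over the four visits and applies it at Week 52. If the true slope is the same at each visit, nothing is lost. If regression on baseline changes over the year, the Week 52 adjustment uses the wrong slope. Baseline variation that could have been removed then stays in the Week 52 residual.

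Two things are at stake. The first is precision at the only visit tested. The second arises when Week 52 data are missing. SAP 6.4 handles withdrawals under missing at random, which relies on the model having the right conditional mean at Week 52. If dropout depends on baseline and differs between arms, a wrong slope can bias the treatment difference.

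**Working it through.** **The plan's own figure.** SAP 4.3 plans a one-sided t-test at 0.025 with 66 and 33 evaluable subjects, and claims "approximately 90% power to detect a clinically meaningful standardized effect size of 0.7 between the 2 groups". The noncentrality is 0.7 × √(66 × 33 / 99) = 0.7 × √22 = 3.28 with 97 df, giving power 0.902. Also 99 / 0.90 = 110. Both reproduce. This is an unadjusted t-test, so it assumes no covariate gain.

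**Formula.** For complete data with residual covariance S and true slopes β at the four visits, the common slope tends to b = (1′S⁻¹β) / (1′S⁻¹1). Week 52 variance is then multiplied by

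V = 1 + Var(baseline) × (β₅₂ − b)² / σ₅₂².

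**Inputs.** Protocol Table 2, Cohort 1 (n = 10), gives a baseline SD of 96.8 m and an SD of 12-month change of 46.5 m. The latter is taken as the Week 52 residual SD, so the ratio is 96.8² / 46.5² = 9370 / 2162 = 4.334. Everything else is assumed: the drift (slope at Week 12 to slope at Week 52, linear in visit order), the earlier-visit SDs and the correlations.

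**Flat SDs.** Here b is the mean slope, so β₅₂ − b is half the drift and V − 1 = 4.334 × (drift / 2)².

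**Rising SDs.** Take, for illustration, 35, 40, 44 and 46.5 m with a common correlation of 0.7. The weights 1′S⁻¹ / (1′S⁻¹1) are 0.712, 0.280, 0.056 and −0.048. For slopes 0, −0.067, −0.133, −0.20, b = −(0.280 × 0.067 + 0.056 × 0.133 − 0.048 × 0.20) = −0.0166. Then V − 1 = 4.334 × 0.1834² = 14.6%, and it scales with drift squared.

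**Cohort 1 SD pattern.** Take 52.2, 40.8 and 46.5 m at Months 6, 9 and 12 for Weeks 26, 38 and 52, with Week 12 assumed equal to Month 6. Correlations are 0.6–0.8 exchangeable, or first-order autoregressive 0.8.

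| Assumed drift | Cohort 1 SDs: extra variance | Flat SDs: extra variance (power) | Rising SDs: extra variance (power) |
|---|---|---|---|
| 0.10 | 0.1–0.7% | 1.1% (89.9%) | 3.6% (89.1%) |
| 0.20 | 0.3–2.6% | 4.3% (88.9%) | 14.6% (85.9%) |
| 0.30 | 0.7–5.9% | 9.8% (87.3%) | 32.8% (80.5%) |

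Power divides the noncentrality by √V and reads 0.7 as relative to the Week 52 residual SD. Other settings (baseline SD up to 120 m, Week 52 residual SD down to 40 m, other correlations) widen the range. It becomes about 0–9% for a drift of 0.10, and reaches 68% for 0.30 at the extreme.

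**Simulation, complete data.** 1,500 runs, 99 subjects, 2:1 within baseline bands, baseline SD 97 m, residual SD rising to 46.5 m, true effect 0.7 × 46.5 = 32.55 m:

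| Drift | SE, common slope | SE, by visit | Power, common | Power, by visit |
|---|---|---|---|---|
| 0 | 9.86 m | 9.89 m | 0.903 | 0.901 |
| 0.10 | 10.07 m | 9.91 m | 0.888 | 0.891 |
| 0.20 | 10.59 m | 9.91 m | 0.865 | 0.895 |
| 0.30 | 11.41 m | 9.90 m | 0.822 | 0.898 |

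Mean estimates matched 32.55 m within Monte Carlo error in both models. Under the null, one-sided rejection rates for the common slope were 0.029 (drift 0.10) and 0.020 (drift 0.20), against 0.029 and 0.025 by visit. Monte Carlo error is about 0.4 points for these and 0.8 points for power.

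**Simulation, dropout.** 300 runs, 110 subjects, rising SDs, same true effect. Assumed dropout was about 20% in control, likelier at low baseline, and 3% in the active arm, about 9% overall. With slopes −0.03 to −0.18, the mean was 34.9 m with a common slope and 32.6 m by visit. With slopes 0 to −0.30, it was 36.4 m and 32.5 m. The differences of 2.3 m and 3.9 m have Monte Carlo SEs of 0.2 and 0.3 m. A separate check gave about 2–5 m over the same drifts. With equal dropout in both arms there was no clear bias.

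**The case against.** The strongest case is that nothing in the documents shows the slope to drift. One common source of a negative baseline slope, measurement error in baseline, enters every change score alike and so gives a constant slope. Averaging two baseline tests also reduces that error. The larger losses need residual SD to rise over visits, yet the SDs in Protocol Table 2 do not rise: 52.2, 40.8, 46.5 m in Cohort 1 and 29.4, 23.1, 29.1 m in Cohort 3. A slope of −0.30 at Week 52 would have baseline explaining 0.30² × 9370 / (0.30² × 9370 + 2162) = 28% of Week 52 variance, which is a stress case. Randomization is stratified on baseline 6MWD, Week 52 missingness is expected below 10% (SAP 8.2), and withdrawn subjects are asked back for an end-of-study visit. The SAP also prespecifies the time-by-baseline model and a Week 52 ANCOVA with its own slope.

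Most of this stands, and it governs the size. A reader might infer that variance is expected to be some 4–11% too high. The documents do not support any expected figure, because they give no slope by visit. A reader might also infer that the primary test is invalid. With complete data it is not.

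What does not stand is that the exploratory and supportive analyses settle the matter. They can reveal a drift but cannot change the primary result, and adding the term after seeing them would be data-driven. The ANCOVA also differs in its handling of missing data, so a gap between it and the MMRM could not be put down to the slope alone.

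**Conclusion.** The constraint is plain in the SAP text and code. Its cost is conditional on drift. For a drift up to about 0.10 the loss is minor: about 0–9% in variance, at most around 2 power points. For 0.30 it runs from almost nothing (Cohort 1 SD pattern) to well over 10% (rising SDs). These figures rest on SDs from 10 subjects and on assumed slopes and correlations.

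This is a point about efficiency, with one qualification: a bias of roughly 2–5 m is possible when drift of 0.15–0.30, rising residual SD, and dropout that is both baseline-related and unbalanced between arms occur together. That compares with a standard error near 10 m. The recommendation rests on asymmetry: the term costs next to nothing if it proves unnecessary and protects the Week 52 comparison if it is needed. It is an optional improvement and not a defect that undermines the primary analysis.

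**What to change.** Before database lock:

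- Add baseline 6MWD-by-visit to the primary model in SAP 8.5.1.
- Add BASE*AVISIT to the MODEL statement of the Appendix 3 MMRM code.
- Remove time-by-baseline 6MWD from the exploratory list in 8.5.1, since the primary model would then contain it.

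The cost is a change of SAP wording and about 3 degrees of freedom (four slopes in place of one). If there is no drift, the standard error rises by well under 1% to about 1%; it went from 9.86 to 9.89 m, or 0.3%, in the simulation above. No new data are needed, and SAP section 2 allows revision until lock. The case made here is for baseline 6MWD only; visit-specific effects of other covariates would need their own justification.

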8.5.1.1. Supportive Analyses for the Primary Efficacy Endpoint and % Predicted FVC

The following supportive analyses will be performed:

Table 6: Supportive Analyses for the 6MWD and % Predicted FVC

	Primary Endpoint (6MWD)	% Predicted FVC
1	ANCOVA at Week 52 on ITT-LOCF	MMRM analysis on ITT-OBS
2	Rate of change in 6MWD based on 12-month slopes	Rate of change in % predicted FVC based on 12-month slopes

Abbreviations: 6MWD = 6-minute walk distance; ANCOVA = analysis of covariance; FVC = forced vital capacity; ITT-LOCF = intent-to-treat population with missing data replaced by the last available value; ITT-OBS = intent-to-treat population that includes all available, observed data without any missing data imputation at Week 52; MMRM = mixed-effect model for repeated measures

In addition, note that as a supportive analysis, each of the other key secondary endpoints will be analyzed using an MMRM analysis on the ITT-OBS population as described in Section 8.3.2.

Details for the supportive analyses are as follows:

- MMRM analysis: This is based on the ITT-OBS population, similar to what has been described for the primary endpoint analysis in Section 8.5.1. There is no need to explore the treatment-by-covariate interaction tests in using MMRM as supportive analysis for the key secondary endpoints.
- Rate of change using ANCOVA on the ITT-OBS population based on the 12-month slopes of the 6MWD assessments (ie, change in 6MWD per month), where the slope is estimated for each subject using a simple linear regression of the observed values. The mean slopes are then compared between the 2 treatment groups adjusting for the baseline value (continuous) and ERT status, as well as baseline age, gender, baseline height, and baseline weight. All the relevant LS estimates (including the LS means for each treatment group, LS mean difference, 95% CI for the LS mean difference, SE, and p-value for comparing the 2 treatment groups) will be provided.

8.5.1.2. Sensitivity Analysis for the Primary Endpoint and % Predicted FVC

The following sensitivity analyses will be considered for the primary endpoint and % predicted FVC.

Table 7: Sensitivity Analyses for the 6MWD and % Predicted FVC

	Primary Endpoint (6MWD)	First Key Secondary Endpoint (% Predicted FVC)
1	Nonparametric randomization-based covariance analysis on ITT-LOCF at Week 52 (if Shapiro-Wilk p-value < 0.01)	Nonparametric randomization-based covariance analysis on ITT-LOCF at Week 52 (if Shapiro-Wilk p-value < 0.01)
2	MMRM analysis incorporating the handling of intercurrent events	ANCOVA incorporating the handling of intercurrent events
3	ANCOVA on the per-protocol population 1 (PP1)	ANCOVA on the per-protocol population 2 (PP2)
4	ANCOVA on ITT-OBS, using the % predicted 6MWD	ANCOVA on ITT-LOCF for the subset of subjects with baseline % predicted FVC value < 85%, vs ≥ 85%; MMRM analyses in ITT-OBS for the subset of subjects with baseline % predicted FVC value < 85%, vs ≥ 85%
5	Randomization test applied to test statistics from the ANCOVA model	Randomization test applied to test statistics from the ANCOVA model

Table 7: Sensitivity Analyses for the 6MWD and % Predicted FVC (Continued)

	Primary Endpoint (6MWD)	First Key Secondary Endpoint (% Predicted FVC)
6	ANCOVA based on ITT-LOCF where externally studentized residuals that are large (eg, > 3) in magnitude (absolute value) are considered as outliers and are removed from the analysis	ANCOVA based on ITT-LOCF where externally studentized residuals that are large (eg, > 3) in magnitude (absolute value) are considered as outliers and are removed from the analysis

Abbreviations: 6MWD = 6-minute walk distance; ANCOVA = analysis of covariance; FVC = forced vital capacity; ITT-LOCF = intent-to-treat population with missing data replaced by the last available value; ITT-OBS = intent-to-treat population that includes all available, observed data without any missing data imputation at Week 52

Details of the sensitivity analyses are as follows:

- Nonparametric randomization-based covariance analysis (nonparametric ANCOVA): This analysis is based on [Koch, Tangen et al. 1998](#) and [LaVange, Durham et al. 2005](#). The SAS/IML[®] (Interactive Matrix Language) implementation of this procedure via the NPARCOV3 macro ([Zink and Koch 2012](#)) will be used. For this method, the ERT status (naïve or experienced) will be specified as STRATA, and baseline value, baseline age, gender, height, and weight will be specified as COVARIATES. The categorical variable (ie, gender) will be recoded as a numeric variable. No missing values are allowed in this macro. Due to the potential for smaller ERT-naïve stratum size, the weighted estimates will be combined across strata prior to covariance adjustment. The covariance matrix calculated under the alternative hypothesis will be used for statistical test to compare between the treatment groups. The relevant results including estimates of the treatment difference, SE, p-value for the treatment comparison, and the 95% confidence interval for the treatment difference will be provided. This is an ITT-LOCF analysis at Week 52, unless otherwise specified.
 - As stated in Section 8.2, this nonparametric method will be used as a sensitivity analysis for the primary endpoint only if the normality assumption for the primary MMRM analysis model is notably violated with the Shapiro-Wilk test p-value < 0.01.
 - This sensitivity analysis will also be used for the % predicted FVC if the normality assumption for the ANCOVA model on the ITT-LOCF population is violated with the Shapiro-Wilk test p-value < 0.01.
 - This nonparametric method will be used to compare the biomarker endpoints at Week 52 between the treatment groups based on the ITT-LOCF population.
- ANCOVA that incorporates the handling of the intercurrent events: This model will be adjusted for the baseline value (continuous) and ERT status, as well as baseline age, gender, baseline height, and baseline weight. See Section 6.4 for the list of intercurrent events.
- ANCOVA applied to the PP population: This model will be adjusted for the baseline value (continuous) and ERT status, as well as baseline age, gender, baseline height, and baseline weight to compare between the 2 treatment groups.

- ANCOVA for % predicted 6MWD: ANCOVA using the change from baseline to Week 52 in % predicted 6MWD, where the % predicted 6MWD is calculated using the [Enright and Sherrill 1998](#) reference equations. This analysis will be performed on observed data (ITT-OBS) and the model will be adjusted for baseline 6MWD (as a continuous variable) and ERT status to compare between the 2 treatment groups. The baseline age, gender, height, and weight will not be included as covariates in this ANCOVA analysis because they are already incorporated in the calculation of the % predicted 6MWD values.
- ANCOVA for the subset of subjects with baseline % predicted FVC value < 85% and the subset with baseline value $\geq 85\%$. This analysis will be performed on the ITT-LOCF population.
- MMRM analysis for the subset of subjects with baseline % predicted FVC value < 85% and the subset with baseline value $\geq 85\%$. This analysis will be performed on the ITT-OBS population.
- Randomization test applied to ANCOVA: Analysis using a randomization test applied to test statistics obtained from the ANCOVA model adjusted for baseline 6MWD (as a continuous variable), ERT status, baseline age, gender, baseline height, and baseline weight to compare between the 2 treatment groups. The p-value for comparing between the 2 treatment groups will be provided. This analysis will be performed on the ITT-LOCF population.

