4.4. Randomization and Stratification

Although this is a multicenter trial, the randomization was not stratified by center. The following 2 risk factors were identified as key prognostic factors, and therefore randomization was stratified according to these:

1. Baseline 6MWD (categorized as: 75 to < 150 meters, 150 to < 400 meters, ≥ 400 meters)
2. ERT status (categorized as: ERT-experienced versus ERT-naïve)

The randomization schedule was generated and administered centrally by Almac Clinical Technologies (Almac), independent of the sponsor's project team. This centralized block

randomization procedure was used to balance the above risk factors, (1) to reduce bias and increase the precision of statistical inference, and (2) to allow various planned and unplanned subset analyses. The randomization ratio was 2:1 (ATB200/AT2221 to alglucosidase alfa/placebo), fixed. Approximately 30 ERT-naïve subjects were planned to be enrolled.

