8. ANALYSIS OF EFFICACY

8.1. General Considerations

The Statistical Analysis System (SAS[®]) software version 9.4 (or the latest version at the time of the analysis) and R software will be used for all statistical procedures and analyses.

In general, where basic summary statistics are needed, continuous variables will be summarized using descriptive statistics (n, mean, SD, median, Q1, Q3, minimum, and maximum); categorical variables will be summarized using number and percentage. For basic summaries involving the change from baseline, a 95% confidence interval (CI) for the mean difference will also be provided.

All inferential statistical tests for the primary and key secondary efficacy endpoints will be 1-sided and will be performed at the alpha level of 0.025, unless otherwise specified.

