8.8.6. Analysis of Pharmacodynamic Endpoints

For the pharmacodynamic endpoints/biomarkers (CK and urinary Hex4), the change from baseline and percent change from baseline at each visit will be summarized by treatment group. A line plot over time of the mean \pm SE for the change and percent change from baseline will be provided by treatment group. The change from baseline to Week 52 will be compared between treatment groups using the nonparametric randomization-based covariance analysis described in Section 8.5.1.2. Analysis will be performed on the ITT-LOCF population.

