8.9. Subgroup Analyses

Subgroup analyses by age group, gender, and race (using all available categories) will be performed for the primary endpoint and the change from baseline to Week 52 in % predicted FVC.

In addition, the following subgroups will be analyzed for the primary endpoint and the change from baseline to Week 52 in % predicted FVC, unless otherwise specified:

- ERT status (categorized as: ERT-experienced versus ERT-naïve)
This subgroup analysis will apply to the primary and key secondary endpoints, % predicted SVC, as well as for the overall adverse event (AE) overview table, summary of treatment-emergent AEs by system organ class and by preferred term, and PD endpoints.
- Baseline 6MWD (categorized as: 75 to < 150 meters, 150 to < 400 meters, ≥ 400 meters)
Note that for this subgroup analysis, categories may be collapsed depending on the actual number of subjects in each category, eg, 75 to < 150 meters and 150 to < 400 meters may be combined into 75 to < 400 meters.
- Baseline 6MWD < *median value*, baseline 6MWD ≥ *median value*
- Baseline FVC < *median value*, baseline FVC ≥ *median value*
- Regions (North/South America, Europe, Asia Pacific)
- ERT duration categorized as: 2 to < 3, 3 to < 5, and ≥ 5 years
- History of IARs (Yes, No)

All subgroup analysis results will be presented by forest plots. The p-values for the treatment-by-subgroup interactions will be presented together in a tabular form.

Note that subgroup analyses will not be performed if the size of the specified subgroup category is small and the analyses will not be meaningful.

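### The nonparametric covariance analysis, the only stated test for CK and Hex4, pairs the alternative-hypothesis covariance matrix with five covariates and is anti-conservative at this sample size

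*SAP*

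**What the plan says.** SAP 8.5.1.2 sets up the method as follows: "the ERT status (naïve or experienced) will be specified as STRATA", and "baseline value, baseline age, gender, height, and weight will be specified as COVARIATES". Because the ERT-naïve stratum may be small, "the weighted estimates will be combined across strata prior to covariance adjustment". The test itself is defined by "The covariance matrix calculated under the alternative hypothesis will be used for statistical test to compare between the treatment groups". The same paragraph asks for the estimate, standard error, p-value and 95% confidence interval. It mentions no small-sample correction or exact reference distribution.

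The method has two uses:

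- **6MWD and % predicted FVC.** It is a sensitivity analysis, run only if the Shapiro-Wilk p-value is below 0.01 (SAP 8.2 and 8.5.1.2). Table 7, row 5, separately lists a randomization test on the ANCOVA statistic for both endpoints, without that condition.
- **CK and urinary Hex4.** The change to Week 52 "will be compared between treatment groups using the nonparametric randomization-based covariance analysis described in Section 8.5.1.2". No normality condition applies and no second test is listed.

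SAP 8.9 says of the ERT-status subgroup: "This subgroup analysis will apply to the primary and key secondary endpoints, % predicted SVC". The same sentence goes on to include the pharmacodynamic endpoints. SAP 4.4 plans about 30 ERT-naïve subjects, and "The randomization ratio was 2:1 (ATB200/AT2221 to alglucosidase alfa/placebo), fixed".

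**The concern.** The alternative-hypothesis matrix estimates variability separately within each arm. Here it must supply the variance of the outcome difference and also the coefficients for five covariates. When the control arm is small, the adjusted variance comes out too low and the adjustment itself adds noise that the formula does not count. Both push the test statistic outward, and referring it to a normal distribution corrects neither.

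Combining strata before adjustment helps the full-sample analysis. It does nothing if the ERT-naïve subjects, with about 10 controls, are analysed alone.

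At stake is how the biomarker p-values are read, since the effect on biomarkers is a listed secondary objective. For 6MWD and FVC, a robustness check that rejects too easily gives weak reassurance when it agrees with the main analysis.

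**Working it through.** **Inputs from the documents.** Two ERT strata, five covariates and strata combined before adjustment (SAP 8.5.1.2); 2:1 allocation and about 30 ERT-naïve subjects, hence 20:10 (SAP 4.4); 66 + 33 = 99 evaluable and about 110 randomized (SAP 4.3). For the primary and key secondary endpoints, tests "will be 1-sided and will be performed at the alpha level of 0.025"; SAP 8.4 uses the same level for other secondary endpoints. No level is stated for the biomarkers, so two-sided 5% is used here, with one-sided rates alongside.

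**Assumptions not in the documents.** Alternative-hypothesis covariance S1/n1 + S2/n2; null-hypothesis covariance S(1/n1 + 1/n2), with S taken over both arms; stratum weights n1·n2/(n1+n2); normal reference; all five covariates kept in the ERT-naïve subgroup unless stated.

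**The plan's own figure.** The SAP gives no error rate for this method. Its sample size does reproduce: the noncentral t with 97 df, 66 versus 33 and effect size 0.7 gives power 0.902 (SAP: about 90%), and 99/0.9 = 110.

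**Statistic.** With d the combined vector of mean differences and V its covariance: b = d_y − V_yx V_xx⁻¹ d_x, var(b) = V_yy − V_yx V_xx⁻¹ V_xy. Reject if |b|/√var(b) > 1.96.

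**Simulated two-sided rejection under no effect** (100,000 trials per setting, normal outcomes):

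| Setting | Alternative matrix | Null matrix |
|---|---|---|
| 99 subjects (20:10 + 46:23) | 7.5% | 4.9% |
| 110 subjects (20:10 + 53:27) | 7.1% | 4.9% |
| ERT-naïve 20:10 | 15.8% | 4.8% |
| ERT-naïve 18:9 | 17.7% | 4.7% |
| ERT-naïve 24:12 | 13.4% | 4.7% |

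At one-sided 0.025 the alternative matrix gives about 3.6-3.7% overall and 8.0% in ERT-naïve subjects. Over heavy-tailed and skewed outcomes the two-sided rate is 6.7-7.9% overall and 15.5-16.1% in ERT-naïve subjects; the null matrix stays at 4.3-5.2%. With skewed outcomes the two tails are unequal, and one full-sample tail can be near nominal.

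**Which ingredient drives it** (alternative matrix, 30,000 trials):

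| Covariates | 99 subjects | ERT-naïve 20:10 |
|---|---|---|
| 1 | 5.9% | 8.1% |
| 3 | 6.4% | 11.8% |
| 5 | 7.8% | 16.0% |

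With no covariates the rates are 5.2-5.8% overall and about 6-7% in ERT-naïve subjects.

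**Rough hand check.** Effective df of the within-arm matrix at 20:10: (1/20 + 1/10)² / [(1/20)²/19 + (1/10)²/9] = 0.0225/0.001243 = 18.1. Five covariates shrink the estimated variance by about (18.1 − 5)/18.1 = 0.72 and inflate the true one by about 1 + 5/(18.1 − 6) = 1.41. The ratio is 1.41/0.72 ≈ 1.95, and 1.96/√1.95 = 1.40 has a two-sided normal tail of about 16%.

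At 99 subjects the stratum weights are 6.67/22 = 0.303 and 15.33/22 = 0.697. The four variance components are 0.303²/20, 0.303²/10, 0.697²/46 and 0.697²/23, and the same formula gives about 62 df. The ratio is then (1 + 5/56)/(57/62) ≈ 1.18, and the tail about 7%. This is only an approximation, but it shows the mechanism.

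**Interval coverage.** A nominal 95% interval from the alternative matrix covers about 92-93% overall and about 84% in ERT-naïve subjects.

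**Unequal spread** (full sample, 10,000 trials, two-sided):

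| Control SD relative to treatment | Null matrix | Alternative matrix |
|---|---|---|
| 0.5 times | 1.8% | 6.2% |
| 1.5 times | 7.6% | 7.1% |
| 2 times | 10.0% | 7.4% |

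In ERT-naïve subjects at 2 times: null 9.5%, alternative 18.6%.

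**The case against.** The strongest reply has four parts.

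**Cause.** The alternative matrix is a legitimate choice. It keeps p-value and interval consistent with each other, and without covariates its size is nearly nominal. This stands: a reader might infer that the matrix alone is at fault, and the covariate counts above show that it is not.

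**Scope.** 6MWD and FVC already have an unconditional randomization test in Table 7, and the nonparametric analysis is only conditional for them. This also stands, and it narrows the point mainly to CK and Hex4. Those two endpoints lie outside the family-wise error control of SAP 8.4.

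**The subgroup figure.** A reader might take 16% as what the plan will deliver for ERT-naïve biomarkers. The documents do not go that far. SAP 8.9 names neither this method nor its covariates for subgroups, ERT status cannot serve as a stratum within one ERT group, and small subgroups may be dropped. The figure comes from reading 8.8.6 with 8.9 and keeping all five covariates. The full-sample inflation does not depend on that reading.

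**Remedy.** The null matrix is not safe in every setting, as the unequal-spread table shows. It holds its level when treatment has no effect and the arms are exchangeable; it can fail when the means are equal but the control arm is much more variable. This stands and must be disclosed. Changing the p-value alone would also leave the interval too narrow, and SAP 8.9 presents subgroup results as forest plots, which normally show intervals.

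None of this removes the anti-conservatism of the only stated biomarker test.

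**Conclusion.** The point holds in limited form. As specified, and under the stated assumptions about covariance forms, weights and reference distribution, the analysis rejects about 7-8% of the time at nominal two-sided 5% in the full sample. If the five-covariate analysis is carried into the ERT-naïve subgroup at about 20:10, it rejects about 16% of the time. The cause is the combination of within-arm covariance, several covariates and a small control arm.

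The practical consequence is mainly for CK and urinary Hex4, overall and by ERT status. A reader might infer that the trial's main efficacy conclusion is exposed. It is not: the primary 6MWD analysis is an MMRM, the key secondary hierarchy uses ANCOVA, and neither takes a p-value from this method. The SAP defers to a published macro and papers that were not available for this check, so a correction documented there but not in the SAP would change the figures.

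**What to change.** 1. In SAP 8.5.1.2, take the p-value from the null-hypothesis covariance matrix, with strata combined as now. Alternatively, extend the randomization test already in that section to CK and Hex4, re-allocating within ERT stratum. Apply the choice overall and by ERT status. Either route targets the no-effect null; the null matrix gave about 4.3-5% size with exchangeable arms.
2. In SAP 8.9, name the method and covariates for the biomarker subgroups. In ERT-naïve subjects use fewer covariates, for example the baseline value only. With one covariate the alternative-matrix interval covers about 92% (100 − 8) instead of about 84%.
3. Label intervals from the alternative-hypothesis matrix as large-sample.

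**Cost.** One analysis setting and a few SAP sentences before database lock. Full-sample power at 0.7 SD is 91% with the null matrix, against a nominally higher 93% that reflects the inflated test. Two downsides should be written down: the p-value and interval can disagree near the boundary, and the null-matrix test is not robust if the control arm is much more variable (about 8% overall at 1.5 times the SD and 10% at 2 times).
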